#### Amendment for telephone option

If video connection is not possible due to technical issues (e.g., bandwidth connectivity issues, software problems, hardware issues) research staff will conduct the intervention session via telephone. Staff will follow the same protocol as described for VVC visits.

Measures collected during intervention:

A urine sample will be collected from participants at the first intervention session. The urine sample will be tested for benzodiazepines and zolpidem to confirm the participant's use/nonuse of these hypnotics. The following measures will be collected weekly throughout the intervention for participants in both study groups.

Clinical Institute Withdrawal Assessment Scale - Benzodiazepines (CIWA-B): This 22-item instrument includes patient symptoms and clinical observations (e.g., tremor) to assess and monitor the type and severity of symptoms of benzodiazepine withdrawal.

*Vital signs:* These physical examination measurements will be taken weekly: blood pressure, pulse, respiratory rate.

*Insomnia Severity Index (ISI):* The ISI is a 7-item instrument that measures perceived severity of insomnia symptoms (total score ranges from 0 to 28).

Epworth Sleepiness Scale (ESS): This 8-item questionnaire assesses general level of daytime sleepiness.

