#### Exclusion criteria:

ligh risk for complications in outpatient hypnotic discontinuation program:

- · Seizure disorder
- Supratherapeutic/high baseline hypnotic dose (> diazepam-equivalent of 8 mg/night). Note that for individuals on > 1 of the targeted hypnotics, total baseline dose in diazepam-equivalents will be calculated & if > 8 mg/night, individual will be excluded.
- · High risk of complicated withdrawal; benzodiazepine intoxication or current or past symptoms of complicated benzodiazepine/alcohol withdrawal (e.g., seizure, delirium at baseline)
- · Polydrug use (e.g., chronic high dose opioids)
- Unable to keep study medications in secure location
- · Evidence of prescription fraud (e.g., multiple prescriptions for same drug filled at VA and non-VA pharmacies, diversion)

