## Eligibility determination for randomization

The final determination of eligibility will take place during a weekly meeting of the investigators. At least one physician ([name] or [name]) and at least one sleep psychologist ([name]) will participate at these meetings. During this "pre-randomization review" meeting, individuals who no longer meet the hypnotic criteria at the baseline assessment will be excluded. Individuals adherent to sleep-disordered breathing therapy and restless legs syndrome (RLS) therapy or with insomnia symptoms incompletely explained by RLS will be considered for intervention, as would be done in clinical practice. Individuals with insomnia symptoms due to circadian rhythm sleep disorders or inadequate opportunity for sleep will be excluded.

Participants with an apnea-hypopnea index ≥ 30 (from home sleep apne testing device such as WatchPAT) will not be eligible for randomization. Participants with an apnea-hypopnea index between 15 and 29.99 (moderate sleep apnea) and with daytime sleepiness (Epworth Sleepiness Scale score > 10) will also not be eligible for randomization. Participants with an apnea-hypopnea index between 15 and 29.99 and no daytime sleepiness will be eligible for randomization. We will inform participants with an apnea-hypopnea index > 15 that they may have sleep apnea and, with their permission, will initiate a consult to the VA GLAHS Sleep Center, or inform their primary care provider.

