#### Randomization

Individuals who complete the baseline assessment and meet all inclusion/exclusion criteria will be randomly assigned to one of the two intervention groups: MTcap (N=66) or SGT+CBTI (N=66). Both interventions are described below. Randomization procedures will follow the CONSORT criteria for randomized trials. Stratified

randomization will be used to ensure that both groups are balanced in baseline hypnotic drug type half-life (i.e., temazepam/zolpidem; alprazolam/lorazepam; clonazepam) and gender. The study statistician will generate the stratified randomization sequence. A set of envelopes containing the group assignment will be generated and stored in a secure file drawer accessible only authorized staff. Once final eligibility is determined, the data manager will open the next envelope in sequence within the appropriate stratum.

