# Amendment for telehealth option

Urine sample: Participants who receive the intervention by VVC/telephone will be asked to go to the VA clinical lab to provide a urine sample prior to the first intervention session.

Vital signs: The interventionist will assess respiratory rate and observe the participant measure their blood pressure and pulse via VVC at each session.

Daily sleep and habits diary: Participants will use the diary to record bedtime, wake time, total sleep time, time to fall asleep, time awake at night, number of awakenings, napping, exercise, alcohol use. Participants in the MTcap group only will also record their perceived hypnotic dose taken and their daytime function and sleep quality.

- MTcap (Masked Taper plus cognitive behavioral therapy-augmented program):
  - a. Hypnotic taper protocol: Participants will receive encapsulated hypnotics in a blister taper pack prepared by a non-VA compounding pharmacy. Participants will be informed that gradual dose reduction will occur during the program, but they will be blinded to the actual dose they receive each day. The planned rate of reduction of hypnotic will be about 25% per week. The final taper pack will consist of 4 placebo capsules (nights 1-4) and 3 empty blisters (nights 5-7). This planned rate of taper would yield a taper length similar to those reported in other studies, where the average length of taper was 49 days (range 6.5 to 84 days).
  - b. Cognitive behavioral therapy for insomnia-augmented program: The 8 sessions will incorporate the key components of CBTI (sleep restriction, stimulus control, cognitive restructuring, targeted sleep hygiene) and CBT targeting hypnotic withdrawal. Using the masked doses as a CBT tool, we will add exercises and concepts designed to address and alter expectations for hypnotics. A daily sleep/perceived hypnotic dose diary will be used as a tool for challenging expectancies about hypnotics, refining treatment recommendations, and adjusting the weekly plan.

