# Extended taper plan

We have identified specific situations when the taper plan may need to be modified:

- a. Withdrawal symptoms/extended taper required: The taper may be extended up to a maximum of 16 weeks if the participant has withdrawal symptoms or cannot tolerate the scheduled taper, based upon changes in several of the CIWA-B items and vital signs, along with the patient's, interventionist's, and study physicians' judgments. In the MTcap group, an extended taper may be achieved by giving a duplicate 7-day blister pack (e.g., plateauing the doses until the participant is ready to move to the next blister pack). In the SGT+CBTI group, participants will be instructed to repeat a particular week in the printed taper schedule. Participants will continue to be monitored with weekly CIWA-B, vital signs, and the interventionist will review and reinforce key content of the intervention.
- b. Hypnotic dosed as "prn" at baseline: Taper schedules for participants who used their hypnotic "as needed" at baseline will be adjusted so that the starting week's total weekly hypnotic dose does not exceed the participants' total weekly baseline hypnotic dose.

For the MTcap group, the capsules on the predetermined drug-free days will be filled with an inert filler substance. The participants will still be instructed to take the capsule on a scheduled based nightly, not as needed. The use of capsules will ensure that the participant is not exposed to the drug more frequently than the baseline exposure. An increase in adherence to the taper protocol is one rationale for using capsules filled with inert filler substance rather than instructing participants not to take any capsule at all (i.e., similar to oral contraceptive inert pills that are provided in the monthly oral contraceptive pill pack). Another rationale for using insert capsules is related to our study's objective, which aims to develop an intervention for reducing placebo effects, such as the effects related to the conditioned response of taking the drug and attributing sleep and daytime function—which are known to vary from day to day—to the act of taking the pill.

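### In person, the urine test of hypnotic use comes after randomisation, so intake is not biochemically confirmed when eligibility is decided

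*Combined protocol and SAP*

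**What the plan says.** All references are to the combined protocol and SAP.

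- **Eligibility.** Under Eligibility determination for randomization, the weekly pre-randomisation review applies this rule: "individuals who no longer meet the hypnotic criteria at the baseline assessment will be excluded". The exclusion criteria in Table 1 also list "Evidence of prescription fraud (e.g., multiple prescriptions for same drug filled at VA and non-VA pharmacies, diversion".
- **Allocation.** Under Randomization, "Individuals who complete the baseline assessment and meet all inclusion/exclusion criteria will be randomly assigned to one of the two intervention groups". The data manager opens the next envelope in the stratum once eligibility is final.
- **Evidence before allocation.** The telephone screen asks about hypnotic use and nights per week. The Baseline Assessment adds prescription data from CPRS and CURES. Table 2 marks a medication log at baseline for the actigraphy week.
- **Urine, in person.** Under the measures collected during the intervention, "A urine sample will be collected from participants at the first intervention session". Its purpose is given as: "The urine sample will be tested for benzodiazepines and zolpidem to confirm the participant's use/nonuse of these hypnotics".
- **Urine, telehealth.** Participants who receive the intervention remotely "will be asked to go to the VA clinical lab to provide a urine sample prior to the first intervention session".
- **Outcome.** The Primary Analysis Plan analyses H1a as a yes/no outcome by logistic regression, under intention-to-treat. It states no condition on verified use at entry.

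The baseline assessment does not include urine, and no section says what follows a negative first result.

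**The concern.** The protocol treats urine as the way to confirm whether someone is taking the drug. In person, that confirmation arrives when it can no longer inform who is randomised. CPRS and CURES show what was prescribed, not what was swallowed, and the log and screening answers are self-reported. A person who fills prescriptions but does not take the drug, and reports otherwise, looks eligible on every source the review has. Diversion is an exclusion, and it is the case these sources are least able to detect.

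Follow-up urine does not repair this. It is collected to confirm reported discontinuation, and a person who was never using would also test negative and look like a confirmed success. Such participants add apparent successes that neither programme produced, and so shrink the arm difference that Aim 1 is designed to detect.

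**Working it through.** **Order of events, in person.** Screening; baseline visits with log and prescription records; pre-randomisation review; envelope opened; session 1, where urine is collected and study medication is handed over. The result comes after allocation. For telehealth, the sample and the mailed medication both precede session 1, but the text does not order the sample against the envelope.

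**Inputs from the Primary Analysis Plan.** 132 randomised, 13% dropout, about 57 per arm, two-sided α = 0.05, power 0.80, control discontinuation 59% to 63%, stated detectable difference 21% to 26%.

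**The plan's own figures.** 132 × 0.87 = 114.8, so 114 completers reproduces. For the detectable difference I used the two-proportion normal approximation with pooled null variance:

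Power = Φ{ [(p₂ − p₁) − 1.96·√(2p̄(1 − p̄)/n)] / √([p₁(1 − p₁) + p₂(1 − p₂)]/n) }, where p̄ = (p₁ + p₂)/2.

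At n = 57 per arm, 80% power needs 23.6 points (control 59%) or 22.7 points (control 63%). Both lie inside the stated range. Its endpoints do not reproduce with one consistent two-sided method, but that is a separate matter.

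**Starting point.** At a mid-range control rate of 61%, 80% power needs an MTcap rate of 84.2%, a difference of 23.2 points.

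**Dilution.** Let f be the share of undetected non-users in each arm, all counted as discontinued. Each observed rate becomes p′ = f + (1 − f)p, so the difference shrinks by the factor (1 − f). The documents give no f; the values below are assumptions.

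| f | Control | MTcap | Difference (points) | Power |
|---|---|---|---|---|
| 0 | 61.0% | 84.2% | 23.2 | 80% |
| 5% | 0.05 + 0.95 × 0.61 = 63.0% | 85.0% | 22.0 | 77% |
| 10% | 0.10 + 0.90 × 0.61 = 64.9% | 85.8% | 20.9 | 74% |
| 15% | 0.15 + 0.85 × 0.61 = 66.9% | 86.5% | 19.7 | 71% |

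Control rates of 59% and 63% give power within about half a percentage point of each row.

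**Scale in participants.** Across control rates of 59% and 63%, restoring 80% power needs 62 per arm at f = 5%, 66 to 67 at 10%, and 71 to 72 at 15%. Dividing the totals by 0.87 and rounding up gives 143, 152 to 155, and 164 to 166 randomised, against 132 planned.

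**The case against.** The case for leaving the plan alone has several sound parts.

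- **Non-users can be excluded.** A reader might infer from the urine timing that they cannot. The documents do not support that: the review removes anyone found from the screen, log or records to be no longer using. Prescribers are also contacted before randomisation. Only people who look eligible on all of these remain, which is a smaller group.
- **One sample is weak evidence.** Use on two nights a week qualifies, as-needed users are included, and no detection window is given. A negative does not prove non-use, and a positive does not prove use at the qualifying frequency. This stands, and it is why the result should support the review and not act as a gate.
- **Scoring is inferred.** The plan does not say how a baseline non-user is scored. Counting all of them as discontinued is the natural reading of an unconditioned yes/no outcome, but some might take the study hypnotic and continue.
- **Bias.** A reader might think that unequal numbers of non-users across arms would bias the estimate. Under randomisation, chance imbalance is sampling error, which the test and interval already reflect.
- **Starting exposure.** The rule that the "starting week's total weekly hypnotic dose does not exceed the participants' total weekly baseline hypnotic dose" might be read as a general principle that unverified intake defeats. It is written only for participants whose hypnotic was taken as needed at baseline, so it cannot carry that argument.
- **Timing is a trade-off.** A sample at session 1 records use at the start of the taper; an earlier one is separated from it by review, prescriber contact, compounding and delivery.

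None of this removes the central gap: in person, the one biochemical test of intake before treatment cannot inform eligibility, and no rule covers a negative result.

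**Conclusion.** The point holds as a cheap improvement, not as a flaw that invalidates Aim 1. For in-person participants the order is explicit in the text; for telehealth participants it is left unstated. The expected consequence is dilution: about 3, 6 or 9 percentage points of power at assumed shares of 5%, 10% or 15%, equal in both arms. The plan sets power at 80% and mentions no allowance for this loss.

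The figures rest on four assumptions: the share itself, which has no source in the documents; every such participant counting as discontinued; planning rates of 59% to 63% not already including people of this kind; and an unadjusted comparison of completers standing in for the planned covariate-adjusted, multiply imputed model. If the share is near zero, so is the loss.

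**What to change.** 1. Collect the existing urine sample before the envelope is opened, either at the second baseline visit or once the review has cleared all other criteria. For telehealth, state that the existing laboratory trip comes before randomisation.
2. Give the result to the pre-randomisation review as supporting evidence for the use and diversion criteria. State that a negative prompts a check of last use and is not an automatic exclusion.
3. If the timing cannot be moved, keep every randomised participant in the primary analysis and prespecify an H1a sensitivity analysis by first-urine result. Removing people after randomisation on that result would undermine intention-to-treat.

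The cost is a short amendment. Some samples will be spent on people who are then not randomised. This matters most for the second-baseline-visit option, since up to 600 may be enrolled for 132 randomised. The later option limits testing but may add a trip for in-person participants. Under either option randomisation waits for the result, and the sample sits further from the start of the taper.

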# Amendment for telehealth option

Urine sample: Participants who receive the intervention by VVC/telephone will be asked to go to the VA clinical lab to provide a urine sample prior to the first intervention session.

Vital signs: The interventionist will assess respiratory rate and observe the participant measure their blood pressure and pulse via VVC at each session.

Daily sleep and habits diary: Participants will use the diary to record bedtime, wake time, total sleep time, time to fall asleep, time awake at night, number of awakenings, napping, exercise, alcohol use. Participants in the MTcap group only will also record their perceived hypnotic dose taken and their daytime function and sleep quality.

- MTcap (Masked Taper plus cognitive behavioral therapy-augmented program):
  - a. Hypnotic taper protocol: Participants will receive encapsulated hypnotics in a blister taper pack prepared by a non-VA compounding pharmacy. Participants will be informed that gradual dose reduction will occur during the program, but they will be blinded to the actual dose they receive each day. The planned rate of reduction of hypnotic will be about 25% per week. The final taper pack will consist of 4 placebo capsules (nights 1-4) and 3 empty blisters (nights 5-7). This planned rate of taper would yield a taper length similar to those reported in other studies, where the average length of taper was 49 days (range 6.5 to 84 days).
  - b. Cognitive behavioral therapy for insomnia-augmented program: The 8 sessions will incorporate the key components of CBTI (sleep restriction, stimulus control, cognitive restructuring, targeted sleep hygiene) and CBT targeting hypnotic withdrawal. Using the masked doses as a CBT tool, we will add exercises and concepts designed to address and alter expectations for hypnotics. A daily sleep/perceived hypnotic dose diary will be used as a tool for challenging expectancies about hypnotics, refining treatment recommendations, and adjusting the weekly plan.

#### SGT+CBTI:

- a. Hypnotic taper protocol: Participants will receive hypnotics in a traditional medication container prepared by a non-VA compounding pharmacy. Participants will also receive a printed taper schedule (see attached Taper Schedule) that reduces the hypnotic using the same schedule as the MTcap group. Each participant will be given a pill cutter so they can cut pills in half or into quarters as directed. A printed taper schedule is routinely used in VA clinical practice to assist patients in reducing hypnotic use. An exception to this protocol will occur if the prescribed medication is temazepam. This medication only comes in capsule form, so it cannot be cut into halves or quarters. Consequently, the participant will receive two difference strengths of temazepam (e.g., 15mg and 7.5mg) in two separately labeled bottles. Rather than cutting the higher strength capsule in half, participants will take the lower strength capsule. This is the taper method that is used clinically for temazepam.
- b. Cognitive behavioral therapy for insomnia: Participants will receive standard CBTI (i.e., stimulus control, sleep restriction, targeting maladaptive beliefs about sleep, sleep hygiene, and relaxation techniques),

and will not be provided with the extra exercises and tools that the MTcap group will receive. The sleep diary that participants will complete will be slightly different from the MTcap sleep diary.

# Extended taper plan

We have identified specific situations when the taper plan may need to be modified:

- a. Withdrawal symptoms/extended taper required: The taper may be extended up to a maximum of 16 weeks if the participant has withdrawal symptoms or cannot tolerate the scheduled taper, based upon changes in several of the CIWA-B items and vital signs, along with the patient's, interventionist's, and study physicians' judgments. In the MTcap group, an extended taper may be achieved by giving a duplicate 7-day blister pack (e.g., plateauing the doses until the participant is ready to move to the next blister pack). In the SGT+CBTI group, participants will be instructed to repeat a particular week in the printed taper schedule. Participants will continue to be monitored with weekly CIWA-B, vital signs, and the interventionist will review and reinforce key content of the intervention.
- b. Hypnotic dosed as "prn" at baseline: Taper schedules for participants who used their hypnotic "as needed" at baseline will be adjusted so that the starting week's total weekly hypnotic dose does not exceed the participants' total weekly baseline hypnotic dose.

For the MTcap group, the capsules on the predetermined drug-free days will be filled with an inert filler substance. The participants will still be instructed to take the capsule on a scheduled based nightly, not as needed. The use of capsules will ensure that the participant is not exposed to the drug more frequently than the baseline exposure. An increase in adherence to the taper protocol is one rationale for using capsules filled with inert filler substance rather than instructing participants not to take any capsule at all (i.e., similar to oral contraceptive inert pills that are provided in the monthly oral contraceptive pill pack). Another rationale for using insert capsules is related to our study's objective, which aims to develop an intervention for reducing placebo effects, such as the effects related to the conditioned response of taking the drug and attributing sleep and daytime function—which are known to vary from day to day—to the act of taking the pill.

For the SGT+CBTI (supervised gradual taper + CBTI) group, the paper taper schedule will indicate which days of the week the participant should and should not take the hypnotic. For example, Mondays, Wednesdays, Fridays, and Saturdays may be deemed drug days, while Tuesdays, Thursdays, and Sundays may be deemed drug-free days. The gradual tapering of drug doses on the drug days will occur over the two-month period. The drug-free days will be clearly marked on the taper schedule. A progressive increase in the number of drug-free days will occur during the taper.

c. More than 1 hypnotic at baseline: Participants who use >1 of the target hypnotics will be tapered off the targeted hypnotics simultaneously using two different blister packs.

